14.2.4. Clinical Data Recording

Each participant will have a clinical file (source data) and eCRF, (for protocol specific data) into which relevant data will be recorded. A log of names, signatures and initials of all staff authorized to enter data into a participant's Clinic File and eCRF will be kept in the site study file.

Upon completion of each study visit, all eCRF data will be reviewed internally by the Study Site for omissions or apparent errors so that these can be corrected without delay. Any corrections made after the review and signature of the PI will be noted in the audit trail and will require re-authorization (electronic sign off) by the PI.

All deviations from this study protocol will be documented in the trial master file and included in the FCSR. An assessment of the significance of each protocol deviation will be discussed in the FCSR.

14.3. Record Retention

All source data, clinical records and laboratory data relating to the study will be retained in the archive of the Study Site for a minimum of 15 years after the completion of the study in compliance with TGA annotations to [CPMP/ICH/135/95](#). Data will be available for retrospective review or audit by arrangement with the Chief Executive Officer of the Study Site. Written agreement from the sponsor must precede destruction of the same.

14.4. Biological Samples

Biological samples will be retained for the time required for assessment for analysis, and may then be discarded.

14.5. Shipment Procedures

The site staff will be responsible for shipment of samples to the sponsor nominated bioanalytical laboratories for testing. All samples will be securely packed in containers provided by the shipping vendor. These will be shipped as per the procedures of the vendor together with completed shipment forms.

14.6. Monitoring

It is the sponsor's responsibility to ensure that the study is monitored in accordance with the requirements of [ICH GCP](#). The conduct of the study will be reviewed internally by the Study Site in accordance with the Study Site SOPs and [ICH GCP](#) guidelines. The trial will be monitored according to the sponsor's SOPs and all significant protocol deviations shall be reported to the sponsor and Bellberry HREC/IRB/HRPO using CNS or Fast-Track SOPs.

14.7. Reporting and Communication of Results

The data management, statistical and medical writing team appointed by the sponsor will collaborate to provide a detailed FCSR upon conclusion of the study. This will include appendices of all Tables, Listings and Figures generated during the analyses of data. The sponsor undertakes to ensure that all safety observations made during the conduct of the trial are documented in this report.

Publication and reporting of results and outcomes of this trial will be accurate and honest, undertaken with integrity and transparency and in accordance with the relevant clauses outlined in the Agreement between the clinical sites and Fast-Track. All manuscripts will need to be reviewed and approved by USAMMDA and 60P before submission. The sponsor recognizes that the PI has a responsibility to ensure that results of scientific interest arising from the clinical trial are appropriately published and disseminated. Publication of results will be presented to fair peer-review. Authorship will be given to all persons providing significant input into the conception, design, and execution or reporting of the research according to NHMRC guidelines ([NHMRC 2007b](#)). No person who is an author, consistent with this definition, will be excluded as an author without his/her permission in writing. Authorship will be discussed between researchers prior to study commencement (or as soon as possible thereafter) and reviewed whenever there are changes in participation. Acknowledgment will be given to the study participants and staff, and collaborating institutions and hospitals and other individuals and organizations providing finance or facilities. In any press releases, publications or presentations, the sponsor's financial contribution to the study and its participation in the collaboration and the trial site, shall be expressly acknowledged. The sponsor agrees that the Linear Clinical Research, in particular the PI, will be entitled to access all the de-identified clinical trial data upon completion of the study. Data will not be released publicly until the manuscript is accepted for publication. In the case of no publication, information will only be released to the public and media in accordance with the Linear Clinical Research's corporate media strategy policy.

As the IND holder and sponsor, 60P will register the trial on the National Library of Medicine's Clinical Trials Registry on the world wide web at <http://www.clinicaltrials.gov>.

In addition, upon study completion and finalization of the study report the results of this trial will be either submitted for publication in an open access journal and/or posted in a publicly accessible database of clinical trial results.

However, the PI undertakes not to make any publication or release pertaining to the study and/or results of the study without the sponsor's prior written consent, being understood that the sponsor will not unreasonably withhold its approval.

The investigator shall not use the name(s) of the sponsor and/or of its employees in advertising or promotional material or publication without the prior written consent of the sponsor. The sponsor shall not use the name(s) of the investigator and/or the collaborators in

advertising or promotional material or publication without having received his/her and/or their prior written consent(s).

The sponsor has the right to publish the results of the study at any time provided the PI has provided input into the manuscript within a 30-day time frame from request.

14.8. Discontinuation of the Study

The sponsor, PI, HREC/IRB and Regulatory Authorities independently reserve the right to discontinue the study at any time for safety or other reasons. This will be done in consultation with the sponsor where practical. In the event of premature trial termination or suspension, the above-mentioned parties will be notified in writing by the terminator/suspender stating the reasons for early termination or suspension (with the exception of the sponsor's responsibility for notifying the Regulatory Authorities). After such a decision, the sponsor and the investigator will ensure that adequate consideration is given to the protection of the participants' interest and safety. All ongoing participants will be followed up for a minimum of 65-75 days after administration of tafenoquine and will be scheduled for an early discontinuation visit or EOS evaluation visit (whichever is applicable). At this visit all assessments scheduled for the EOS evaluations (Week 64) will be performed as described in [section 8.4](#).

14.9. Study Audit

Audits may be carried out by sponsor quality assurance representatives, local authorities or authorities to whom information on this study has been submitted. All documents pertinent to this study must be made available for such inspections after adequate notice of intention to audit.

APPENDIX 1. SD-OCT FINDING

OCT CST – automated segmentation performed by the Heidelberg Spectralis OCT device will generate an average thickness of the retina in the central 1 mm zone, measured from top of the Internal Limiting Membrane (ILM) to bottom of the RPE (in μm).

OCT TMV – automated segmentation performed by the Heidelberg Spectralis OCT device will generate an average thickness of the retina in the central 6 mm zone, from the top of ILM to the bottom of RPE which provides a volume measurement of the central 6 mm zone (in cubic millimeters).

OCT Parafoveal (inner ring) and perifoveal (outer ring) Retinal Thickness – automated segmentation performed by the Heidelberg Spectralis OCT device will generate an average thickness of the retina in a rim region between the central 1 mm and 3 mm diameter rings and 3 and 6 mm diameter rings, measured from top of the ILM to bottom of the RPE (in μm).

OCT Subretinal Fluid Thickness – manual measure of greatest linear height of any sub retinal fluid (if present) (in μm).

***En face* OCT ellipsoid zone disruption** – manual measurement of the greatest linear extent of ellipsoid layer loss due to foveal photoreceptor damage based on en face OCT scans segmented to the level of ellipsoid zone. Results will be reported as normal or abnormal.

***En face* OCT retinal pigment epithelium layer disruption** – manual measurement of the greatest linear extent of loss of RPE layer due to drug toxicity based on en face OCT scans segmented to the level of RPE layer. Results will be reported as normal or abnormal.

***En face* OCT interdigitation zone disruption** – manual measurement of the greatest linear extent of preserved interdigitating layer due to perifoveal photoreceptor damage based on en face OCT scans segmented to the level of interdigitating layer. Results will be reported as normal or abnormal.

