5.3. Rationale of Dose Selection and Dosing Regimen

Previous clinical studies support a Recommended Regimen for malaria prophylaxis of a loading dose of 200 mg once daily for 3 days before travel to a malarious area, followed by weekly 200 mg maintenance doses while in the malarious area and an additional dose of 200 mg at one week of return from travel.

The tafenoquine dose regimen chosen for this study is based on safety and tolerability data, PK data from Phase 1 and 2 studies and efficacy data from dose-ranging chemoprophylaxis studies. The tafenoquine 200 mg dose is regarded as the highest, well-tolerated dose that achieves a protective tafenoquine concentration of 80 ng/mL in 95% of the sample population. Moreover, this is the tafenoquine recommended regimen for malaria prophylaxis approved by the FDA. Results from the placebo arm will be used as a comparator for spontaneous occurrence of ophthalmic and psychiatric effects.

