 - Urine sampling for determination of the following parameters:
 - Urinalysis (dipstick and urine microscopy if blood, leukocyte esterase, or nitrates are positive); and
 - Urine drug screen (amphetamines, methamphetamines, barbiturates, benzodiazepines, cocaine, methadone, opiates, phencyclidine, tetrahydrocannabinols, and tricyclic antidepressants).
 - **Ophthalmic Assessments:** The following ophthalmic tests will be performed at Screening. Given the short period of time between Screening (Visit 1b) and dosing (Week 1, Day 1 [Visit 2]) the ophthalmic data from Screening will be used as the baseline data:

Visit 1b:**Before pupil dilation:**

- BCVA (ETDRS letter score);
- Color vision assessment with FM-100 hue test;
- Mars letter contrast sensitivity test;
- M-chart distortion test; and
- Slit lamp examination.

After pupil dilation:

- MAIA microperimetry. Conducted twice with the first result discarded to minimize learning effect.
 - Heidelberg Spectralis SD-OCT (including wide field macular scan);
 - Heidelberg Spectralis qFAF (set of 3 images to ensure consistency in measurement);
 - Digital photograph of corneal surface (conventional and wide field);
 - Digital photograph of retina (conventional and wide field);
 - Slit lamp retinal examination (pupils dilated) and intraocular pressure (IOP) measurement
- **Psychiatric Assessments**
 - M.I.N.I. English Version 7.0.2.
 - **Eligibility Assessment by Investigators:**
 - Final review of inclusion and exclusion criteria by the investigators to confirm eligibility for enrolment into study;

Participants who complete all screening procedures and satisfy all eligibility criteria will be considered eligible to participate in this study.

If screening laboratory results are abnormal (after repeat tests as appropriate are performed) (e.g., HIV testing), the participant will be referred for appropriate counseling as applicable. If any clinically significant abnormalities are detected during screening, the participant will be referred for follow-up tests to a general practitioner or medical specialist as appropriate.

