- Abnormality found on any of the following ophthalmologic examinations (only the test that revealed an abnormality will be repeated, unless at the discretion of the investigator additional testing is warranted):

- SD-OCT, qFAF, BCVA [ETDRS], FM-100 hue test, Mars letter contrast sensitivity test and M-chart.
- Slit lamp examination and digital photograph of corneal surface (cornea Verticillata) and retinal digital photograph (toxic maculopathy and retinopathy on conventional and wide field device).
- Microperimetry.

Participants will report to the Study Site in the morning.

The following assessments will be performed during this follow-up visit (if required):

- Blood sampling as needed to follow abnormality:
 - CBC and biochemistry;
 - MethHb %;
- Urine sampling as needed to follow abnormality:
 - Urinalysis (dipstick and urine microscopy if blood, leukocyte esterase, or nitrites are positive).
- Ophthalmic Assessments (repeat only if abnormal at Week 64). Abnormal results may need to be further investigated using microperimetry, color vision assessment with FM-100 hue test, Mars letter contrast sensitivity test and M-chart. Corneal deposits and retinal lesions from drug toxicity at Week 64 needed to be monitored by slit lamp examination, SD-OCT (including wide field macula scan), qFAF and photography (conventional and wide field);
- Psychiatric Assessment with M.I.N.I 7.0.2 (repeat if disorders are found at Week 64).
- Assessment with DHI (if participant reports ongoing AE of dizziness or vertigo).

General:

At all follow-up visits, participants will be reminded of the following before leaving the Study Site:

- Study restrictions as described in [Section 6.4](#);
- To return to the Study Site for the following scheduled visit; and
- To contact the Study Site in the interim should they experience AEs or require treatment with any concomitant medications.

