Change from baseline in BCVA, key SD-OCT continuous parameters, and LSEQ component scores will be analyzed by a random intercept mixed model to account for correlation between repeated measures. Treatment effect (difference and 95% CI) on the change from baseline variables will be estimated across study visits.

Specifically, the following assessments will be conducted for secondary safety endpoints, and the extra analyses, if mentioned as below, will be applied.

- Mean change from baseline in key SD-OCT parameters including CST, TMV volume, and parafoveal (inner ring of ETDRS grid) retinal thickness and the proportion of participants with ellipsoid or interdigitating zone disruption. The difference in the proportion of participants with clinically significant ophthalmologic changes (as defined in the primary endpoint) between treatment group and the placebo group will be calculated. In addition, the change from baseline in individual SD-OCT and qFAF parameters listed in [Appendix 1](#) and [Appendix 2](#) will be tabulated and compared between tafenoquine and placebo-treated groups.
- Proportion of participants with abnormal changes from baseline observed on qFAF using the Spectralis HRA+OCT device with grey scale values extracted from these images for statistical analysis using qFAF software (Heidelberg Engineering).
- Mean change from baseline in BCVA. Changes from baseline in BCVA results by the ETDRS chart will be tabulated and compared between the two groups. A clinically significant deterioration is defined as a reduction of more than 4 letters from baseline (Week 1, Day 1 [Visit 2]) of 0.08 logMAR. The M-chart will be used to quantify the severity of the distortion (if detected). An additional analysis of BCVA changes will include the proportion of participants experiencing a 1-4 letter change (less than one line of ETDRS visual acuity change), a 5-9 letter change (1 line, but less than 2-line change), 10-14 letter change (2 lines, less than 3 lines) or 15 or more letter change (3 lines or more) in BCVA from baseline. A ≥ 15 letter (≥ 3 line) or more change in ETDRS BCVA at 4 meters is considered clinically significant.

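### Appendix 1 makes drug causation part of the en face RPE-layer measurement, a secondary item that blinded readers grade and that is compared between arms

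*Combined protocol and SAP*

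**What the plan says.** Appendix 1 lists the SD-OCT parameters. For disruption of the RPE layer on the en face scan it asks for a "manual measurement of the greatest linear extent of loss of RPE layer due to drug toxicity", reported as normal or abnormal. Other entries carry no such condition. Sub-retinal fluid is measured whatever its cause. The ellipsoid entry is a "manual measurement of the greatest linear extent of ellipsoid layer loss due to foveal photoreceptor damage", which names a tissue mechanism and not the study drug.

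Section 12.2.3.2 puts the item into a between-arm analysis: "the change from baseline in individual SD-OCT and qFAF parameters listed in" Appendices 1 and 2 "will be tabulated and compared between tafenoquine and placebo-treated groups". Section 8.1 sets the reference point: "the ophthalmic data from Screening will be used as the baseline data". Section 5.3 gives the purpose of the control arm: "Results from the placebo arm will be used as a comparator for spontaneous occurrence of ophthalmic and psychiatric effects".

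Under Section 9.2.6 the clinical sites make the initial evaluation of the scans. The central reading center, which is not shown the site's result, grades to the outcomes as the protocol defines them. Section 7.6 has all research staff blinded.

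Section 8.5, on Part 3 follow-up, uses similar causal language: "Corneal deposits and retinal lesions from drug toxicity at Week 64 needed to be monitored by slit lamp examination".

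**The concern.** In a randomised, blinded comparison the contrast between arms carries the causal inference, so a measurement should record what is on the scan. A reader following Appendix 1 has to decide first whether a loss is drug-induced, and only then measure it. Nothing in the documents says how a blinded reader would make that decision. What is recorded becomes the rate of loss that a reader attributed to the drug, which is a different quantity from the rate of loss. Spontaneous loss, which Section 5.3 wants the placebo arm to show, is what the wording tells the reader to leave out.

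The tissue matters for this drug. Section 2.1.1.2 reports fundoscopic abnormalities, RPE changes among them, in 27 of 69 tafenoquine and 4 of 17 mefloquine participants in Study 033. Examiners knew of the corneal deposits, and experts could not judge relevance because there was no baseline retinal photography. This trial has baseline imaging and a placebo arm, and a causal filter on an RPE item gives away part of that advantage.

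**Working it through.** The plan gives no figure for this item, so there is none to reproduce. The sample size figures in Section 12.1 rest on the SOSE rate. The five Table 5 parameters that define SOSE do not include the RPE layer, so those figures do not depend on this wording.

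**Text check.**
- Cause is in the definition (Appendix 1), readers grade to the definition (Section 9.2.6), and the result is compared between arms (Section 12.2.3.2). The three together put a causal judgement inside a blinded between-arm measure.
- At Screening no loss can be due to study drug. Read literally, baseline is always normal for this item, and any pre-existing loss goes unrecorded. Exclusion criterion 3 (retinal abnormalities at screening) limits this problem but does nothing for loss that arises later.

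**Illustration.** Let p be the true rate of new RPE-layer loss and s the probability that a reader attributes a loss to the drug. Both are assumptions. The arm size of 300 is from Section 12.1. Recorded rate = p × s; expected recorded count = 300 × p × s.

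*Placebo arm.* With no filter (s = 1), p of 0.5%, 1% and 3% gives 1.5, 3.0 and 9.0 expected cases. With s = 0.5 it gives 0.75, 1.5 and 4.5.

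*Equal filter in both arms, true rates 3% and 1%.* Recorded difference = s × (3% − 1%).

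| s | tafenoquine count | placebo count | difference (points) |
|---|---|---|---|
| 1 | 300 × 0.03 × 1 = 9 | 300 × 0.01 × 1 = 3 | 2.0 |
| 0.5 | 4.5 | 1.5 | 1.0 |
| 0.25 | 2.25 | 0.75 | 0.5 |

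The ratio stays at 3. With no true effect, the expected difference stays at 0. An equal filter therefore costs events and absolute difference but does not create an effect.

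*Unequal filter, no true effect.* Recorded difference = p × (s on tafenoquine − s on placebo). With s = 0.75 and 0.25, p = 1% gives 0.01 × 0.5 = 0.5 points, and p = 3% gives 0.03 × 0.5 = 1.5 points, all of it false. A route to unequal filtering is in the plan: Section 7.7 treats corneal deposits as a sign of tafenoquine exposure, and Section 8.3 has deposits graded at the slit lamp within the same set of eye assessments as the OCT. Section 12.2.3.2 does not say whether the site's or the reading center's grading of this item is analysed.

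**The case against.** The best defence is that the phrase is a loose gloss. All three en face entries follow one template, and the interdigitation entry speaks of preserved layer caused by damage, which cannot work as a measurement condition. Section 12.2.3.1 also has a cause-neutral rule: new or worsened qualitative findings that the blinded reading site considers clinically important count as change. Section 9.2.6 leaves test parameters to an ophthalmology manual that is not among the documents.

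This weakens the point without removing it. The Section 12.2.3.1 rule says when a finding counts as a change, not what is measured. The sister entries name tissue damage; only this one names the drug. A manual may say something different, but a reader told to follow the protocol definition should not have to rely on that.

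Other parts of the defence stand, and they rule out three stronger readings that a reader might infer.
- *The placebo count would be zero and the risk ratio infinite.* That needs readers who know the allocation. Blinded readers would label some placebo losses as toxic.
- *The placebo arm can no longer show spontaneous retinal change.* This is one item, outside Table 5 and not named in the Section 5.2.2 endpoint list. Appendix 2 measures geographic atrophy and abnormal autofluorescence with no cause condition, and retinal photography counts any new abnormality.
- *Section 8.5 restricts Part 3 follow-up to lesions attributed to the drug.* Its entry criterion is any abnormality on the listed eye examinations, and Section 9.2.6 likewise follows abnormal tests without regard to cause. The remaining issue is inconsistent wording.

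**Conclusion.** The point holds for one supplementary secondary parameter. As written, the en face RPE-layer item asks blinded readers to attribute cause before measuring, and its between-arm comparison then estimates something other than the effect on RPE-layer loss. With equal filtering the consequence is lost sensitivity: an assumed 2.0-point difference becomes 1.0 at 50% attribution or 0.5 at 25%. With filtering that differs by arm it is bias: 0.5 to 1.5 points under an assumed 75% versus 25% attribution and background rates of 1% to 3%. These sizes rest wholly on assumed rates. The documents give neither a background rate nor an attribution rate, and they do not show that deposits would in fact sway site readers. The primary SOSE analysis and its sample size are unaffected.

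**What to change.** In Appendix 1, delete the last four words of "manual measurement of the greatest linear extent of loss of RPE layer due to drug toxicity" and record any RPE-layer loss on the en face scan, at Screening and at follow-up, in both arms. Do not add a limit to the ETDRS grid: Appendix 1 sets none for this item, and the SD-OCT includes a wide-field macular scan, so a limit could drop loss outside the grid. Leave opinions on cause to the adverse event assessment, where Section 10.11.2 already places them. Make sure the ophthalmology manual uses the same definition.

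Section 8.5 speaks of retinal lesions from drug toxicity, while its own entry criterion and Section 9.2.6 refer to abnormalities without regard to cause. These passages must be reconciled.

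The cost is a few words of amendment. A few more non-specific findings will be recorded, in both arms.
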